## Statistical Analysis Plan

Sponsor Name: Nitto Denko Corporation  
Sponsor Protocol ID: ND-L02-s0201-005

the corresponding times have not been recorded. Measurements that are obtained after the first date of study treatment will be considered post-baseline values. Change from baseline is defined as (post-baseline value – baseline value).

Time-to-event endpoints will be summarized using Kaplan-Meier (KM) method to estimate the median, and the 25th and 75th percentiles.

The following principles will be applied to all TFLs unless otherwise stated:

Principle	Value
Treatment arm labels and order presented	1. Placebo 2. ND-L02-s0201 45 mg 3. ND-L02-s0201 90 mg 4. Total (if applicable)
Tables	Data in summary tables for safety will be presented by treatment arm, and Total, and visit (where applicable). Data in summary tables for efficacy will be presented by treatment arm.
Listings	All data collected presented by treatment arm, subject, and visit date (where applicable), unless otherwise specified.
Descriptive summary statistics for continuous variables	Number of subjects (n), mean, standard deviation, median, minimum, maximum
Descriptive summary statistics for categorical variables	Frequency counts and percentages [n (%)]
Denominator for percentages	By-visit summaries: number of subjects with non-missing data at the visit assessed in the analysis population of each treatment arm; Other summaries: Number of subjects in the analysis population of each treatment arm, unless specified otherwise.
Include "Missing" as category	Included for demographics and other baseline characteristics when the number of missing is greater than zero for at least one treatment arm. Missing post-baseline values will not be summarized, unless otherwise specified.
Display for percentage	One decimal place, except for 100%
Display for 0 percentages	blank
Display to one more decimal place than collected value	Mean, Median

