## 6. Data Handling

### 6.1 Time points and Visit Windows

Day 1 is defined as the day of first dose of treatment (visit 2). Relative days after Day 1 are calculated as (assessment date – Day 1 date) + 1. Relative days prior to Day 1 are calculated as (assessment date – Day 1 date). The day prior to Day 1 is Day -1.

All data will be analyzed using nominal study visits as defined in the Study Schedule of Assessment and eCRF. Data collected at unscheduled visits will be listed only, except for the following:

- Data from unscheduled visits will be included in the calculation of baseline laboratory values.
- Data from unscheduled visits will be included in the calculation of the worst CTCAE grade or abnormality used in the laboratory shift tables.
- For a nominal visit with a missing measurement, the measurements of the unscheduled visits occurring between this particular visit and the two adjacent visits will be used to assign the analysis value. The closest unscheduled visit value that is not assigned to previous visits will be assigned to this nominal visit.

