### 6.2 Handling of Dropouts, Missing Data, and Outliers

Missing values on FVC, DLCO and DLCO corrected for hemoglobin, HRCT analysis variables, [REDACTED] at Visit 14 (Day 169) will not be imputed. In situations where the efficacy endpoints are missing, all available data will be analyzed with a mixed-effects model for repeated measures (MMRM). To evaluate robustness of results, sensitivity analyses will be performed by imputing missing data using statistical modelling of available data.

Incomplete dates (partial or missing dates) for start date of AEs will be imputed and used to determine treatment-emergent status as follows:

- If the start date of an AE is completely missing, the first dosing date (Day 1) and time will be used for the imputation and the AE will be considered treatment-emergent.
- If the start date of an AE is missing day and month:
  - If the year of the AE start date is the year of the first dosing date, the month and day will be imputed using the month and day of first dosing date;
  - Otherwise, the month and day will be imputed as January 1.
- If the start date of an AE is missing the day only:

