## Statistical Analysis Plan

Sponsor Name: Nitto Denko Corporation  
Sponsor Protocol ID: ND-L02-s0201-005

Study treatment response is defined as a decline in FVC (L and % of predicted) of no more than 10% in the relative change at Visit 14 that is calculated as:

$$\text{Change in FVC L (\%)} = \frac{(\text{FVC L at Visit 14} - \text{FVC L at Baseline})}{\text{FVC L at Baseline}} * 100\%$$

The change in FVC % of predicted (%) will be calculated as:

$$\text{Change in FVC \% of predicted (\%)} = \frac{(\text{FVC \% of predicted at Visit 14} - \text{FVC \% of predicted at Baseline})}{\text{FVC \% of predicted at Baseline}} * 100\%$$

A positive value indicates improvement. Number and percent of subjects responding to treatment will be summarized.

The number and percent of subjects within each treatment arm showing an improvement, and subjects showing a decline of 0% to ≤5%, >5% to ≤10%, and >10% at Visit 14 (day 169) will be summarized by treatment arm. Subjects with an FVC response is defined as improvement in FVC or a decline of ≤10% from baseline FVC value.

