## 8. Changes in Planned Analysis

The following changes from protocol specified statistical analyses are made in this SAP.

Section 3.2 and 7.5.2.4 The efficacy endpoint Time to first acute IPF exacerbation has been updated to Time to first acute IPF exacerbation and death to avoid dependent censoring.

Section 7.5.2.1, 7.5.2.2, 7.5.2.3, and 7.5.5 Analysis of change from baseline in FVC, DLco, HRCT QLF, [REDACTED] will be using random coefficient model instead of ANCOVA. The random coefficient model will handle missing data by making use of all available data include subjects with missing data and no missing value will be imputed.

Section 7.5.3 Sensitivity analysis of FVC will use multiple imputation instead of ANCOVA without missing value imputation.

[REDACTED]

[REDACTED]

[REDACTED]

[REDACTED]

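### The FVC response percentage at Visit 14 has no stated denominator and no rule for death, so an arm that loses its sickest subjects can show a higher response rate

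*SAP*

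**What the plan says.** The proportion of subjects with an FVC response at Visit 14 is a named secondary endpoint (Protocol 13.1.2.1; SAP 3.2). Biological activity is analysed on ITT (Protocol 13.2.4), which is every randomized subject (SAP 5.2).

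SAP 7.5.2.1 computes the relative change from the Visit 14 and baseline values and then states: "Subjects with an FVC response is defined as improvement in FVC or a decline of ≤10% from baseline FVC value". On reporting it says only: "Number and percent of subjects responding to treatment will be summarized". It also tabulates improvement and three bands of decline by treatment arm. Neither sentence gives a denominator or mentions death.

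The general rules come from three places:

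- SAP 6.2: missing FVC values "at Visit 14 (Day 169) will not be imputed".
- SAP 7.1, denominators: "By-visit summaries: number of subjects with non-missing data at the visit assessed in the analysis population of each treatment arm", and alternatively "Other summaries: Number of subjects in the analysis population of each treatment arm, unless specified otherwise".
- SAP 7.1, missing rows: "Missing post-baseline values will not be summarized, unless otherwise specified".

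The multiple imputation in SAP 7.5.3 names change and percent change in FVC, not the response proportion. The other sensitivity analysis there repeats the analyses on the PP population, which adds nobody back.

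**The concern.** Missing Visit 14 spirometry in IPF is unlikely to be unrelated to outcome. Protocol 5.1 gives respiratory failure from progression as the most frequent cause of death, and Protocol 11.2.2.2 foresees subjects deteriorating until testing is not feasible. If such subjects leave both numerator and denominator, the response percentage describes survivors with a measurement, although the stated population is ITT. The arm that loses more of its worst subjects then looks better, and because missing post-baseline rows are suppressed by default, the response table itself would not show the loss.

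The alternative denominator does not settle the matter, because subjects without a value then belong to no category. Two programmers following the SAP could produce different percentages from the same data.

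**Working it through.** **No figure to reproduce.** The documents state no expected response rate, dropout rate or power for this endpoint. The only planning input is about 40 subjects per arm (SAP 2.3; 3 × 40 = 120). Everything below on response and missingness is an assumption, shown over a range.

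**Notation.** n = 40 ITT subjects in the arm, m = subjects with no usable Visit 14 value, r = responders.

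- By-visit rule: p = r/(n − m).
- All-ITT denominator: r/n.
- Gap: r/(n − m) − r/n = p × m/n.

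**Observed response near 80%:**

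| m | r | r/(n − m) | r/n | Gap (points) |
|---|---|---|---|---|
| 2 | 30 | 30/38 = 78.9% | 75.0% | 3.9 |
| 4 | 29 | 29/36 = 80.6% | 72.5% | 8.1 |
| 8 | 26 | 26/32 = 81.25% | 65.0% | 16.25 |
| 10 | 24 | 24/30 = 80.0% | 60.0% | 20.0 |

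**Range.** With observed response near 70% the gap runs from 3.6 points (m = 2, r = 27) to 17.5 (m = 10, r = 21). Near 90% it runs from 4.5 (m = 2, r = 34) to 22.5 (m = 10, r = 27).

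**What happens to a comparison of arms.** This depends on whether loss is unequal.

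- Equal loss and equal response (m = 4, r = 29 in both arms): 80.6% against 80.6% by visit, 72.5% against 72.5% on ITT. The difference is zero either way.
- Equal responder counts, unequal loss (28 and 28; m = 4 and 8): 28/36 = 77.8% against 28/32 = 87.5% by visit, a difference of 9.7 points. On ITT both are 28/40 = 70.0%.
- Unequal in both (placebo m = 2, r = 30; active m = 8, r = 26): active minus placebo is 81.25 − 78.9 = +2.3 points by visit, and 65.0 − 75.0 = −10.0 points on ITT.

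**The other-summaries rule.** Take m = 8 and r = 26. The remaining 32 − 26 = 6 measured subjects declined by more than 10%. Response is 26/40 = 65.0% and the decline row is 6/40 = 15.0%. These sum to 80.0%; the other 8/40 = 20.0% appear in no row.

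**The case against.** **The by-visit reading is not certain.** The SAP never labels the response table a by-visit summary. Section 7.5.2.1 summarizes continuous FVC by arm and visit, but the response categories by arm only. If the other-summaries rule applies, the denominator is already all ITT. This stands: a reader might infer that the plan definitely specifies a completers' percentage, and the text does not go that far. It still leaves the denominator unstated and the missing subjects unclassified.

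**Not everyone who stops treatment is lost.** This also stands in part.

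- SAP 6.1 provides a substitution: "For a nominal visit with a missing measurement, the measurements of the unscheduled visits" between the adjacent visits can supply the value. However, 7.5.2.1 keeps unscheduled results out of FVC summary tables, so its reach here is unclear.
- Protocol 8.4.2 asks those who discontinue to complete ET procedures, and the visit schedule puts ET in the Visit 14 column. SAP 7.5.2.1 does not say whether an ET value counts; the HRCT section, 7.5.2.3, separates the two.
- Protocol 11.2.2.2 uses the most recent PFT when a repeat test is not possible. The readable SAP does not carry this over.

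The problem is therefore confined to subjects who die or have no usable value. It does not extend to every dropout.

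**Losses are visible elsewhere, and the stakes are limited.** Disposition (SAP 7.2) and the mortality and time-to-event endpoints report them. Percent change in FVC, on which response is a cut-point, gets placebo-based multiple imputation. There is no primary efficacy endpoint (SAP 7.5.1) and no test of the response proportion is described. All true, but none of this corrects the percentage itself.

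**SAP 8 is only an analogy.** Time to exacerbation "has been updated to Time to first acute IPF exacerbation and death to avoid dependent censoring". A reader might take this as the sponsor already accepting the present argument. The stated reason concerns censoring in a time-to-event analysis, which is related to a percentage's denominator but not the same.

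**Redaction.** Protocol 13.2.4 and part of SAP 7.5.2.1 cannot be read, so a rule could exist there. The response paragraphs themselves are readable and contain none.

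**Conclusion.** The point holds as an unstated denominator and an absent rule for death in a named secondary endpoint. On the natural reading the response percentage is conditional on having a Visit 14 value; on the alternative reading the categories do not account for all ITT subjects. Neither is satisfactory, and the SAP does not choose.

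The consequence is a potentially biased description. Assuming about 80% observed response and 40 per arm, the by-visit percentage is inflated relative to an all-ITT denominator by about 4 points with 2 missing, and by about 16 to 20 points with 8 to 10 missing. Those counts are assumptions.

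Two stronger conclusions are not supported. One is that the treatment comparison would reverse: this needs unequal loss of the kind assumed in the last example, the documents give no rates, and equal loss with equal response produces no distortion of the difference. The other is that type I error or a decision rule is compromised: no test is attached to this endpoint.

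**What to change.** In SAP 7.5.2.1:

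1. Set the denominator to all ITT subjects in the arm.
2. Count death before Visit 14 as non-response, in a category of *decline >10% or death*.
3. Show *missing, alive* as its own row, so that the rows sum to 100%.
4. State whether ET, unscheduled or most recent PFT values count as Visit 14, and reconcile this with Protocol 11.2.2.2 and SAP 6.1.
5. Report two sensitivity versions: the observed-case percentage, and one that places *missing, alive* in non-response.

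Keeping *missing, alive* separate in the main table is deliberate. Protocol 18.6.2.3 allows a remote Visit 14 during COVID-19 restrictions, and the minimum remote data set in 18.6.2.4 does not include spirometry, so some gaps will be logistical. With an all-ITT denominator the response row is r/n in either layout; what changes is the non-response row. In the example with m = 8 and r = 26, it is (6 + deaths)/40 in the main table and 14/40 = 35.0% in the second sensitivity version.

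This is a cheap improvement: a few sentences and one extra table, with no new data. The downside is that response rates will look lower in every arm with missing values, by p × m/n.

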## Statistical Analysis Plan

Sponsor Name: Nitto Denko Corporation  
Sponsor Protocol ID: ND-L02-s0201-005

Principle	Value
Display to two more decimal places than collected value	Standard Deviation Confidence interval
Display to p-value	P-values will be rounded to 3 decimal places. P-values less than 0.0005 (e.g. 0.0002) will not be rounded to 3 decimal places (e.g. 0.000) but instead be displayed as <0.001.
Date Format	DDMMYYYY
Statistical Analysis	All statistical tests will be conducted at the 2-sided, 0.05 level of significance. There will be no adjustment for multiplicity.

### 7.2 Subject Disposition and Data Sets Analyzed

Subject disposition will be listed and summarized by treatment arm and overall for all randomized subjects and will include the number and percentage of subjects:

- randomized;
- randomized by randomization stratification factor (i.e., standard of care at enrollment);
- included in each analysis population (SAF, ITT, PK1, PK2, and PP).
- completed the study
- discontinued treatment
- primary reason for discontinuation of treatment
- terminated early from the study (terminated before Visit 8 or after visit 8) including early termination due to COVID-19 pandemic.
- primary reason for early termination.

### 7.3 Protocol Deviations

All protocol deviations will be listed. Important protocol deviations leading to exclusion from the PP population will be listed and summarized by treatment arm for the ITT population. Protocol deviations due to COVID-19 will be listed separately.

The deviations leading to exclusion from the PP population will be identified before data are unblinded.

### 7.4 Demographics and Other Baseline Characteristics

Demographic and baseline characteristics will be listed and summarized by treatment arm and overall for the SAF population. Standard descriptive statistics will be presented for the continuous variables of:

- age (years) [as reported in the eCRF];

## Statistical Analysis Plan

Sponsor Name: Nitto Denko Corporation  
Sponsor Protocol ID: ND-L02-s0201-005

- weight (kg);
- height (cm);
- body mass index (kg/m^2) [calculated as (weight/height) where weight is in kg and height is in m];
- systolic blood pressure (mmHg);
- diastolic blood pressure (mmHg);
- body temperature (°C);
- pulse rate (beats/min);
- respiratory rate breaths (breaths/min);
- pulse oximetry (SPO2) (%);
- forced vital capacity (FVC) in L;
- percent predicted FVC (%);
- forced expiratory volume in 1 second (FEV1) in L;
- percent predicted FEV1 (%);
- ratio of FEV1/FVC;
- diffusion capacity of the lung for carbon monoxide (DLco) ;
- percent predicted DLco (%);
- hemoglobin corrected DLco;
- hemoglobin corrected percent predicted DLco (%);
- [REDACTED]
- duration of IPF since diagnosis to start of study treatment (months)
  - calculated as (first dose date-initial IPF diagnosis date+1)/30.4375
- GAP IPF Risk of Mortality: The risk of mortality (1-, 2-, and 3-year risk) will be derived based on baseline data at the start of the treatment period using the Gender, Age, and Physiology (GAP) methodology described in Ley et al, 2012 ([Appendix 1](#));

The total counts and percentages of subjects will be presented for the categorical variables of:

- gender;
- childbearing potential for females
- race;
- ethnicity;
- BMI group [Underweight (below 18.5); Normal (18.5 - 24.9); Overweight (25 - 29.9); Obese (30 and above)]
- smoking history(yes/no)
  - If smoking history is yes, active smoker(yes/no)
- background standard of care (nintedanib, pirfenidone, none);

■

■

## Statistical Analysis Plan

Sponsor Name: Nitto Denko Corporation  
Sponsor Protocol ID: ND-L02-s0201-005

- GAP IPF Stage: The IPF stage will be derived based on baseline data at the start of the treatment period using the Gender, Age, and Physiology (GAP) methodology described in Ley et al, 2012 ([Appendix 1](#));

No formal tests of statistical significance will be performed on the demographic and baseline data.

### 7.4.1 Medical History

Medical history will be coded using the lasted version of Medical Dictionary for Regulatory Activities (MedDRA), per the Data Management Plan, throughout the study. All medical history will be listed, and the number and percentage of subjects with any medical history will be summarized for the SAF population by system organ class (SOC) and preferred term (PT) for each treatment arm and overall.

### 7.4.2 Previous and Concomitant Medications

Medications including COVID-19 vaccination received prior to or concomitantly with study treatment will be coded using the lasted version of WHO Drug Dictionary Anatomical Therapeutic Chemical (ATC) Classification codes, per the Data Management Plan, throughout the study. Only medications taken within 14 days before Visit 1a through end of study will be included in summary table and listing.

Prior medications and concomitant medications are defined as follows:

- Prior medications are those taken and ended within the interval from 14 days before Visit 1a up to the earliest of 24 hours before Visit 1a or date of informed consent.
- Concomitant medications are those taken on or after the earliest of 24 hours before Visit 1a or date of informed consent. Medication taken prior to but ongoing after the earliest of 24 hours before Visit 1a or date of informed consent will be considered concomitant medication.

If a medication cannot be classified as "prior" or "concomitant" for missing/incomplete dates, it will be classified as both prior and concomitant.

Prior medications and concomitant medications will be listed together and summarized separately for SAF populations for each treatment arm and overall.

The number and percentage of patients using each medication will be displayed together with the number and percentage of patients using at least one medication within each therapeutic class (ATC-Level 2), chemical subgroup (ATC-Level 4), and preferred term. Tables will be sorted in descending overall frequency by ATC-Level 2, ATC-Level 4, and preferred term, and then alphabetically.

## Statistical Analysis Plan

Sponsor Name: Nitto Denko Corporation  
Sponsor Protocol ID: ND-L02-s0201-005

[REDACTED]

### 7.5 Efficacy

#### 7.5.1 Primary Efficacy Analysis

No primary efficacy endpoint is identified in the study protocol. Analyses of secondary endpoints for biological activity are described in [Section 7.5.2](#).

#### 7.5.2 Secondary Efficacy Analysis

##### 7.5.2.1 Analyses of FVC

Values of FVC variables described in [Section 3.4.1](#) will be summarized with descriptive statistics by treatment arm and visit for the ITT Population. The summary will include FVC (or percent predicted FVC) values, the change and percentage change from baseline to each post-baseline visit for each parameter. Results from unscheduled visits will not be included in summary tables, but will be included in subject-level listings and statistical model.

A random coefficients model will be used to analyze the rate of decline in FVC (L) from baseline to Visit 14 (Day 169) as well as the absolute change from baseline in FVC at Visit 14 in the ITT Population. [REDACTED]

[REDACTED]

Reporting of model results will include the estimated mean change from baseline, adjusted for baseline FVC and standard of care, at each timepoint [REDACTED] with corresponding 95% CIs. In addition, mean slope (rates of change) of FVC from baseline to Visit 14 (Week 24) for each treatment arm will be estimated along with 95% CIs. Treatment differences between mean slopes and corresponding p-values will be presented. No adjustments for multiple comparisons will be made. Spaghetti plots of individual FVC (L) data over time will be produced for each treatment arm with estimated means from the random coefficient model and 95% CIs at each timepoint [REDACTED] superimposed.

Similar analysis will be repeated for FVC (L) relative change from baseline, absolute and relative change from baseline for percent predicted FVC (%FVC).

## Statistical Analysis Plan

Sponsor Name: Nitto Denko Corporation  
Sponsor Protocol ID: ND-L02-s0201-005

Study treatment response is defined as a decline in FVC (L and % of predicted) of no more than 10% in the relative change at Visit 14 that is calculated as:

$$\text{Change in FVC L (\%)} = \frac{(\text{FVC L at Visit 14} - \text{FVC L at Baseline})}{\text{FVC L at Baseline}} * 100\%$$

The change in FVC % of predicted (%) will be calculated as:

$$\text{Change in FVC \% of predicted (\%)} = \frac{(\text{FVC \% of predicted at Visit 14} - \text{FVC \% of predicted at Baseline})}{\text{FVC \% of predicted at Baseline}} * 100\%$$

A positive value indicates improvement. Number and percent of subjects responding to treatment will be summarized.

The number and percent of subjects within each treatment arm showing an improvement, and subjects showing a decline of 0% to ≤5%, >5% to ≤10%, and >10% at Visit 14 (day 169) will be summarized by treatment arm. Subjects with an FVC response is defined as improvement in FVC or a decline of ≤10% from baseline FVC value.

### 7.5.2.2 Analyses of DLco

Values of DLco variables described in [Section 3.4.2](#) will be summarized with descriptive statistics by treatment arm and visit for the ITT Population. The summary will include the absolute and percent change from baseline to each post-baseline visit for each parameter. Results from unscheduled visits will not be included in summary tables or statistical models, but will be included in subject-level listings.

DLco corrected for hemoglobin and DLco not corrected for hemoglobin will be analyzed similarly as FVC as described in section 7.5.2.1.

